3.3.3. Interruption or Discontinuation of Treatment

A reaction of at least moderate erythema (2) accompanied with mild, but definite edema (1) to a study product observed after the first patch application/irradiation sequence of the Induction Phase may indicate the subject to be pre-sensitized and may cause the discontinuation of the subject from the study.

After the second reading of the Induction Phase, either of the following conditions will require that the study product be applied to a naïve patch site under open patch conditions:

- Reaction of >50% “p” or “p” with no erythema, mild but definite erythema, moderate or severe erythema; or “D” (see [Table 3](#) and [Table 4](#));
- Any reaction of definite erythema (mild, moderate or severe) with definite edema.

Study product may not be relocated more than twice.

If the reactions noted above occur on an irradiation day during the Induction Phase, the sites will not be able to be irradiated. Patches will be relocated at the subject’s next visit.

The 3 weeks of continuous patch contact during the Induction Phase frequently results in tape-related irritation that is exacerbated by warm weather, but which occurs among some individuals irrespective of the season. Tape-related irritation will not be graded as a photosensitivity response at the patch site but will be noted separately on the case report form (CRF). Severe tape-related irritation will necessitate a change in the application site. As above, the application site will only be changed twice and then the subject must be discontinued.

One application/irradiation session may be missed during the Induction Phase. In case of a missed application/irradiation, an additional application/irradiation during Week 4 must be

performed. In this case, no evaluation will be required following irradiation. Only one missed patch application or irradiation is allowed. A subject must be discontinued and considered not complete if more than one application or irradiation is missed.

In accordance with legal requirements and ICH-GCP guidelines, every subject has the right to refuse further participation in the study at any time and without providing reasons (see also [Section 5.3](#)). A subject's participation is to be terminated immediately upon his/her request. The Investigator should seek to obtain the reason and record this on the CRF.

If at the time of refusal, a study product has already been administered, the subject should be advised on follow-up safety investigations. If a subject withdraws from the study, all efforts will be made to complete a final evaluation if possible. Subjects experiencing an AE will be followed until the AE is resolved, a reasonable explanation is provided for the event, or the subject is referred to his/her own primary medical doctor (PMD). The specific AE in question will be recorded on the appropriate CRF.

If a subject develops a serious adverse event (SAE), his/her termination from the study will be considered by the Investigator. Similarly, if the subject develops conditions over the course of the study which would have excluded his/her entry in the study according to the safety-related medical exclusion criteria, he/she must be withdrawn immediately.

The subject may be withdrawn from the study at any time at the discretion of the Investigator for medical reasons and/or due to non-adherence to the treatment scheme and other duties stipulated in the study protocol. The reasons are to be documented on the CRF.

In addition, the Sponsor retains the right to end the study at any time if the study cannot be carried out as agreed upon in the protocol. In case of premature termination or suspension of the study, the Sponsor's study manager will promptly inform the Investigator/institutions and regulatory authorities of the termination or suspension and the reason for that. It is the responsibility of the Principal Investigator (PI) to notify the Institutional Review Board (IRB) in the case of premature termination/suspension.

3.3.4. Withdrawals

The following medical and other reasons justify a premature termination (by subject or Investigator) of any of the study PI.

- Adverse Event/Serious Adverse Event
- Death
- Protocol Violation (e.g. non-compliance)
- Investigator Judgment
- Pregnancy
- Lost to Follow-up
- Withdrawal by Subject
- Study Terminated by Sponsor

- Other

If a subject withdraws from the study, all efforts will be made to complete a final evaluation, if possible. Subjects discontinued for having experienced an AE will be followed until the AE is resolved, a reasonable explanation is provided for the event, or the subject is referred to his/her own PMD. The specific AE in question will be recorded on the appropriate CRF.

3.4. Treatments

3.4.1. Investigational Products and Control

Investigational Products:

MC2-01 Cream

MC2-01 cream contains 0.005% w/w CAL (as anhydride) and 0.064% w/w% BDP and is filled in sealed, collapsible aluminum tubes as primary packaging material. The MC2-01 cream formulation contains 70% oil and 30% aqueous external phase at approximately neutral pH. The oil fully solubilizes the drug substances and provides semi-occlusiveness important for skin penetration, while the aqueous external phase contributes to the skin feel. The cosmetic appearance is a white easily spreadable cream with high oil content that absorbs completely into the skin within few minutes of application.⁸

MC2-01 Vehicle

MC2-01 Vehicle contains no active components.

MC2-01 Cream and MC2-01 Vehicle will each be applied in an amount of 0.2 g to 2 sites (2 cm x 2 cm) on the infrascapular area of the subjects' backs for 24 hours (± 4 hours) under semi-occlusive patch conditions (Webril®). The patches will be secured to the skin with airtight nonporous Blenderm® tape. This will be repeated twice each week during the 3-week Induction Phase, once on Monday during rest week 4 as applicable (if a subject misses a visit and doesn't apply the IPs) and once at Challenge. One application site of each study product will be irradiated and the other will remain non-irradiated.

Lot numbers will be given in the clinical study report.

Manufacturer: DPT Laboratories, Ltd.

[name]
[name]

Control

An untreated irradiated site will serve as a control.

3.4.2. Description of Investigational Products

The IPs (MC2-01 Cream and MC2-01 Vehicle) will be supplied in collapsible aluminum tubes for the clinical study. MC2-01 Cream and MC2-01 Vehicle were manufactured and packaged in accordance with good manufacturing practice (GMP).

3.4.3. Description of Patch Conditions

Material evaluated under semi-occlusive patch conditions is applied to a 2 cm x 2 cm Webril® pad. The pad is affixed to the skin with hypoallergenic tape (Micropore).

Material evaluated under open (non-occlusive) conditions is applied directly to a 2 cm x 2 cm area of the skin, which is then loosely covered by gauze secured on 2 sides with Micropore tape.

3.4.4. Packaging/Labeling

The study product tubes labels will contain, at a minimum, the following information:

- Name and address of the Sponsor
- Protocol number
- Name and address of manufacturer
- Date of manufacture
- Lot / batch number
- Tube contents
- Storage conditions
- Caution statements:
 - “New Drug – Limited by Federal Law to Investigational Use”
 - “Flammable”
 - “Keep out of reach of children”

A full product description can be found in the Investigator's Brochure (IB).⁸

MC2-01 Cream and MC2-01 Vehicle must be stored at 2°-8°C (36°-46°F) in a temperature-controlled cabinet at the clinical site. MC2-01 will not be dispensed to individual subjects during this clinical study but may be stored at temperatures below 25°C (77°F) during the product application visits. The PI will be responsible for the suitable storage of the IPs in compliance with the storage instructions and must restrict access to the investigative personnel only.

3.4.5. Assignment to Treatment

3.4.5.1. Randomization

Each subject who signs an informed consent form (ICF) will be assigned a screening number. If the subject meets all of the inclusion and none of the exclusion criteria, and successfully completes the screening procedures, they will be enrolled in the study. Upon enrollment, each subject will be assigned a unique subject number and receive a randomization code, indicating application placement of the study materials. Each subject in this study will serve as his or her own control. All subjects will receive MC2-01 Cream and MC2-01 Vehicle at adjacent application sites, i.e. study product placement on the left side will be the same as on the right side.

The MC2-01 Cream and MC2-01 Vehicle will be assigned in a randomized sequence to the test sites. The same study material will be applied to the same test site throughout the Induction Phase and to a naïve site at Challenge and Rechallenge Phases (if applicable).

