3. INVESTIGATIONAL PLAN

3.1. Study Design

This will be a randomized, double-blind, single-center, controlled, within-subject comparison study of the investigational products (IPs), MC2-01 Cream, MC2-01 Vehicle, and an untreated irradiated control site in healthy volunteer subjects. A total of 8 application sites (2 cm x 2 cm each) will be marked on the subject's back and distributed so that 4 sites are on one side of the back for induction, and 4 sites are on the other side for challenge patches. The IPs will be applied in two sets. One set of patches on the back will be designated for irradiation after approximately 24 hours (\pm 4 hours) of study product application and the other set will remain non-irradiated. An additional site will be marked on the back during Challenge. The site will receive no treatment but will be irradiated at Challenge to serve as an untreated irradiated control.

A defined area (approximately 50 cm²) on the infrascapular region of each subject's back will be irradiated to determine the minimal erythema dose (MED) of ultraviolet (UV) light.

During the 3-week Induction Phase of the study, 0.2 g of each study product will be applied to 2 sites twice each week (Monday and Thursday) for approximately 24 hours (\pm 4 hours) under semi-occlusive patch conditions (6 applications). After patch removal, all application sites will be evaluated, and one application site of each study product will be irradiated with 2 times the subject's MED using the full Xenon lamp spectrum. The sites will be evaluated by a trained evaluator. All sites will be reevaluated post irradiation, at approximately 48 hours later when irradiated on Tuesdays and at approximately 72 hours later when irradiated on Fridays except when irradiated on the last Friday of the Induction Phase or after the last make-up visit (if required), the sites will not be evaluated because these readings are not used for determination of photosensitization and any response will have subsided by Monday. These procedures will be performed each week for 3 weeks of the Induction Phase. Dermal reactions at the application sites will be evaluated using a visual scale that rates the degree of erythema, edema, and other signs of cutaneous irritation (see [Table 3](#) and [Table 4](#)).

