3.4.5.2. Blinding

The treatments (MC2-01 Cream and MC2-01 Vehicle) will not be blinded to investigative personnel involved in the preparation/application and removal of treatments.

Investigative personnel who are involved in the preparation/application and removal of the treatments will be unblinded and will not perform the evaluation of skin responses. The subjects and the trained evaluator who will be evaluating skin responses will be blinded to IPs and the treatment allocation; however, because of the demarcations/skin coloration remaining on the skin following patch removal, complete blinding of the evaluators cannot be completely assured.

Investigative personnel who are blinded, including the Investigator and trained evaluator involved in the evaluation of responses, will remain blinded during the course of the study until Database Lock and finalization of the Statistical Analysis Plan (SAP).

In the event of an emergency, if possible, the Investigator or designee will contact the Sponsor with notification of the intent to unblind the treatment codes prior to the actual unblinding. If it is not possible to notify the Sponsor prior to the unblinding, the Investigator or designee will contact the Sponsor immediately following the unblinding procedure and follow with a written notification to document the exact manner in which the code was broken and the justification for the unblinding. The Investigator will communicate the treatment identification to only the investigative personnel who require the information to manage the emergency. Unblinding will happen on site at TKL.

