3.5. Visit Schedule and Assessments

3.5.1. Study Procedures and Visit Schedule

Screening

At Screening, the subjects will receive any necessary written and verbal information, and the informed consent of each subject will be obtained. Demographic data (including Fitzpatrick skin type) will be recorded, a medical history will be taken, and previous and concomitant medications will be reviewed. Eligibility will be determined by review of the inclusion/exclusion criteria.

- Any written and verbal information
- Informed consent
- Demographics
- Previous/concomitant medication
- Review of inclusion and exclusion criteria
- Medical history (including lifestyle and habits)
- Evaluation of application site area

Table 1: Fitzpatrick Skin Types

I	Always burns easily, never tans
II	Always burns easily, tans minimally
III	Burns moderately, tans gradually
IV	Burns minimally, always tans well
V	Rarely burns, tans very well
VI	Never burns, deeply pigmented ^{10, 11}

Day 1

On Day 1, all subjects will be questioned regarding the entry criteria and female subjects of childbearing potential will undergo a UPT. If the subject fulfills all of the inclusion and none of the exclusion criteria, he/she will be allowed participation in the study. Concomitant medications and AEs will be reviewed and recorded at this visit.

Upon enrollment, each subject will be assigned a unique subject number and receive a randomization code, indicating application placement of the study products.

A baseline evaluation of the patch sites will be performed immediately prior to application of the patches to ensure that no conditions, markings, or coloration of the skin will interfere with interpretation of the study results.

A total of 4 application sites (2 cm x 2 cm each) will be planned on each subject's back. Prior to patching, sites will be marked with site numbers. The distance between the patches will be no less than one centimeter. The numbering of the test sites will remain the same throughout the study. The sites will be marked with an indelible, surgical marker.

Minimal Erythema Dose Determination

On Day 1, subjects will have an area of skin on their back, approximately 50 cm², divided into 6 equal sites marked with a surgical marker. The duration of UVA/UVB irradiation for minimal

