3.5.7. Safety Assessments

3.5.7.1. Patch Test Site Evaluations

For both Induction and Challenge Phases, after 24 hours (± 4 hours) of product application, all sites will be evaluated, and one application site of each product and the additional untreated site will be irradiated. The sites will be examined for dermal reactions at approximately 24 hours, 48 hours, and 72 hours post-irradiation.

The scores in [Table 3](#) will be used to express the response observed at the time of examination and will be recorded on the subjects' CRFs. The score will be used for statistical analysis.

Additional response notations are presented in [Table 4](#). The same evaluator (where possible) should perform the assessment throughout (from Induction to Rechallenge) the study.

Table 3: Response Scores

Response	Symbol	Numerical Equivalent Score
Erythema		
No reaction	-	0
Mild, but definite erythema	+	1
Moderate erythema	++	2
Marked/severe erythema	+++	3
Edema		
No reaction	-	0
Mild, but definite edema	**	1
Definite edema with erosion/vesiculation	***	2

Table 4: Notations

Response/Comment	Notation
Hyperpigmentation	Hr
Hypopigmentation	Ho
Vesiculation	V
Papular response	p
Papulovesicular response	pv
Damage to epidermis: oozing, crusting, and/or superficial erosions	D
Itching	I
Spreading of reaction beyond patch study site (ie, reaction where material did not contact skin)	S
Follicular irritation with or without pustule formation (folliculitis)	f
Subject absent	X
Patch dislodged	PD
Not patched	NP
No reaction	0

The readings will be made under a standardized white light source.

The 3-week period of patch contact during the Induction Phase may result in tape-related irritation in some individuals. Tape related irritation will not be graded as an irritant response at the patch site but will be noted separately on the CRF.

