**MC2 Therapeutics**  
Protocol No. MC2-01-C10

Page X of Y

Listing 16.1.7: Subject Randomization  
All Randomized Subjects

Subject Number	Informed Consent Date	Met all Inclusion/Exclusion Criteria?	Randomization Date	Randomization Number	Randomization [1]	
					Site 1	Site 2
XX	XXXX-XX-XX	Yes	XXXX-XX-XX	XX	A	B
XX	XXXX-XX-XX	Yes	XXXX-XX-XX	XX	B	A
XX	XXXX-XX-XX	Yes	XXXX-XX-XX	XX	A	B
XX	XXXX-XX-XX	Yes	XXXX-XX-XX	XX	B	A
XX	XXXX-XX-XX	Yes	XXXX-XX-XX	XX	B	A

[1] A = MC2-01 cream; B = MC2-01 vehicle

Generated on XX/XX/XX:XXXX by XXXXXXXX / Uses: XXXX, XXXX

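### No independent cream/vehicle order is described for Challenge, so an order guessed during Induction could carry into the readings that decide photosensitization

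*Protocol*

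**What the plan says.** Under Protocol 3.4.5.1, on enrollment each subject will "receive a randomization code, indicating application placement of the study materials". One code is mentioned, issued once. The same section adds that "study product placement on the left side will be the same as on the right side". On what happens after Induction it says: "The same study material will be applied to the same test site throughout the Induction Phase and to a naïve site at Challenge and Rechallenge" (if applicable). It does not say in what order the products go on the naïve sites.

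Protocol 3.1, repeated in SAP Section 3, divides the back so that "4 sites are on one side of the back for induction, and 4 sites are on the other side for challenge patches". Protocol 3.5.1 (Day 1) adds: "The numbering of the test sites will remain the same throughout the study". The shell of SAP Listing 16.1.7 shows one randomization entry per subject, with a Site 1 and a Site 2 column holding A-B or B-A. It has no column for Challenge or Rechallenge.

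On blinding, Protocol 3.4.5.2 keeps the unblinded application staff apart from the evaluators, but warns that "because of the demarcations/skin coloration remaining on the skin following patch removal, complete blinding of the evaluators cannot be completely assured". Protocol 3.5.7.1 asks for continuity of reading: "The same evaluator (where possible) should perform the assessment throughout (from Induction to Rechallenge) the study". The Investigator diagnoses photosensitization from the Challenge reactions. Protocol 4.6.2 and SAP 11.8 both state that no statistical test decides it.

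**The concern.** There are only two possible orders, so the code is one bit per subject. If Challenge repeats the Induction order, anyone who has worked out that bit during three weeks of readings already knows which Challenge site carries the cream.

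A clue during Induction is plausible. The vehicle has no active components. Protocol 1.1.2 names irritation from calcipotriene and atrophy from betamethasone dipropionate as the main local effects seen in non-clinical work. Each product is applied six times under patch, with irradiation of one site after each application, and the notation list provides for changes in pigmentation.

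Challenge answers the primary question, through visual grades and a clinical judgement. Rechallenge may also be called at the Investigator's discretion. With 50 evaluable subjects, one changed classification moves the incidence by 1/50 = 2 percentage points. Protocol 3.4.5.2 keeps the Investigator and evaluator blinded until database lock, so the sponsor regards this blind as worth protecting.

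**Working it through.** The plan gives no figure to reproduce. The sample size of 50 is justified by convention, without power inputs, and neither document gives a rate at which the blind might fail. The check has two parts.

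**What the text fixes**

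1. Protocol 3.4.5.1 mentions one code per subject and says that left and right placement match.
2. Protocol 3.1 is the only text that assigns the two sides of the back, and it assigns them to Induction and Challenge. Taken with step 1, the Challenge order equals the Induction order.
3. There is a second reading. SAP 11.7 and 11.8 use the word side for irradiated versus non-irradiated sites. On that usage, 3.4.5.1 says only that the cream/vehicle order is the same in both sets.
4. On the second reading the Challenge order is not stated. The single enrollment code, the constant site numbering and the single A/B entry in Listing 16.1.7 still show no independent draw.

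**How much a guess could carry over**

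Let g be the probability that an Induction guess of the order is right. This is an assumption. A value of 0.5 is pure chance.

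- Shared code: the Challenge order equals the Induction order, so P(right at Challenge) = g.
- Independent 1:1 code: P(right at Challenge) = g × 0.5 + (1 − g) × 0.5 = 0.5 for every g.
- Excess over chance among 50 subjects under the shared code = 50 × (g − 0.5).

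| Assumed g | Correct, shared code (50 × g) | Correct, independent code | Excess over chance, shared code |
|---|---|---|---|
| 0.5 | 25 | 25 | 0 |
| 0.6 | 30 | 25 | 5 |
| 0.8 | 40 | 25 | 15 |
| 0.9 | 45 | 25 | 20 |

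Correct guesses are not the same as known placements. Suppose a fraction k of subjects is truly identified and the rest are coin flips. Then g = k + 0.5 × (1 − k), so k = 2g − 1. For g = 0.5, 0.6, 0.8 and 0.9, the number truly identified is 50 × k = 0, 10, 30 and 40.

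None of these counts is a number of altered grades or diagnoses. The documents give no basis for that further step.

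**The case against.** The case on the other side has five parts.

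- **The copied order is not stated outright.** A reader might infer that the protocol orders the Induction placement to be repeated at Challenge. It does not say so in those terms: left and right are undefined, and the SAP's use of side gives a real alternative. Listing 16.1.7 is also a mock shell, so its missing columns are weak evidence on their own. This stands as a limit on wording. It does not produce an independent Challenge order anywhere in the documents.
- **The blinding caveat is general.** A reader might take it as an admission that Induction sites carry marks that identify the product. It speaks of marks after patch removal, names no phase, and does not say that the marks differ by product. It applies equally after the Challenge patches come off. A new code therefore cannot be said to restore the blind at Challenge. It cuts off only what was learned earlier.
- **The diagnostic guidelines limit the harm.** Under Protocol 3.5.7.1, a reaction is suspect only when erythema and edema are both seen. If the irradiated and non-irradiated sites both react, the irradiated site must be at least one grade stronger on Rechallenge. That contrast is within product, so knowing cream from vehicle does not create it. This stands in part: the guidelines are described as generally considered, and they rest on the same visual grades.
- **Time and staffing help.** Challenge follows 10 to 17 days of rest. Protocol 3.1 expects responses to the last Induction irradiation to have gone by the following Monday. Evaluator continuity is asked for only where possible. Marks may well fade, although the evaluator's memory or notes need not.
- **The Rechallenge order is not stated at all.** That is true, and it is a reason to state it.

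None of these is a reason for using one order in both phases, and the documents offer none.

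**Conclusion.** The point holds as a cheap improvement to the design. No independent Challenge order is described, and the most natural reading is that the Induction order is reused. With an admittedly imperfect evaluator blind and preferably one evaluator throughout, an order inferred in Induction has a route into the Challenge grades, the decision to rechallenge and the Investigator's diagnosis.

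The size is unknown. On assumed guess accuracies of 50 to 90%, correct guesses at Challenge exceed chance by 0 to 20 of 50 subjects with a shared code, and by 0 with an independent code. At 50% there is no effect.

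A reader might go further and treat 30, 40 or 45 of 50 subjects as unblinded at Challenge. The documents do not support that. Those totals include lucky guesses, the accuracies are assumed, and nothing shows that any grade or diagnosis would change.

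**What to change.** In Protocol 3.4.5.1:

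- Define left and right, and say whether they mean the two sides of the back or the irradiated and non-irradiated sets.
- Keep the same cream/vehicle order across the irradiated and non-irradiated sets within a phase, so that the within-product comparison stays matched for position. Deleting the left/right sentence outright could lose this.
- Draw an independent AB/BA order for Challenge, and another for Rechallenge if it is performed. Only the unblinded application staff should hold these orders.

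In the SAP, add Challenge and Rechallenge columns to Listing 16.1.7.

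The cost is a short amendment and extra columns in the randomization list. Sample size, visits and within-subject comparisons do not change. The downside is that application staff work from a different site map at Challenge, so a placement check is needed when the patches go on. Clues that arise at Challenge itself remain, and the report should say so.

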After 24 hours (± 4 hours) of study product application (eg, Tuesday and Friday), all patches will be removed. The sites will be evaluated using the scoring system detailed in [Section 3.5.7.1](#). One set of patches will be assigned for irradiation and the other will remain non-irradiated, ie, only one application site of each study product will receive irradiation. On all Tuesdays and Fridays, the sites designated for irradiation will be irradiated with 2 times the subject's MED using the full Xenon lamp spectrum.

Adverse events and concomitant medications will be reviewed at each visit and recorded as applicable.

One application/irradiation session may be missed during the Induction Phase. If a subject misses an irradiation session during the Induction Phase, an additional application/irradiation session will be scheduled the Monday of rest period (week 4).

Rest Period (Weeks 4 and 5)

During the Rest Period of approximately 10-17 days, subjects will not receive any application of study materials. An additional application of study product may be applied on the Monday of the

rest period (week 4) if the subject misses an irradiation session during the Induction Phase of the study.

Challenge (Week 6)

On Day 1 of the Challenge Phase, subjects who have completed the Induction Phase and the Rest Period will have study product applications to naïve sites in the same manner as applied during the Induction. As in the Induction Phase, 0.2 g of MC2-01 Cream and MC2-01 Vehicle will each be applied to 4 assigned sites for Challenge for approximately 24 hours (± 4 hours) under semi-occlusive patch conditions. A baseline evaluation of the naïve sites will be performed immediately prior to application of the patches to ensure that no conditions, markings, or coloration of the skin will interfere with interpretation of the study results. The clinical staff will then remove the patches and a trained evaluator will evaluate the test sites. The designated sites and an additional untreated site will be irradiated with 6 J/cm² of UVA (320-400 nm) followed by 0.5 times the MED of UVA/UVB (full-spectrum) irradiation, obtained by using a filtered light source (see [Section 3.5.4](#)). Each site will be evaluated again at approximately 24 hours (± 4 hours), 48 hours (± 4 hours), and 72 hours (± 4 hours) post irradiation.

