### **Local Tolerability Assessments**

The mean numerical equivalent score by subject and treatment, including all scores assigned during induction, will be analyzed in the analysis of variance (ANOVA) with factors subject and treatment. Selected pairwise comparisons will be performed in the context of the ANOVA. Pairs to be compared are: each test sample irradiated versus non-irradiated (MC2-01 cream irradiated versus non-irradiated; vehicle irradiated versus non-irradiated, and untreated control irradiated versus non-irradiated) and all pairwise comparisons on each side (MC2-01 cream versus vehicle; MC2-01 cream versus untreated control; and vehicle versus untreated control; all on both the irradiated and non-irradiated sides).

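### The randomization code sets only the cream/vehicle order; how the irradiated set of sites is chosen is not stated, so the irradiated versus non-irradiated contrast can be confounded with position on the back

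*Protocol*

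**What the plan says.** Protocol 3.4.5.1 states that "The MC2-01 Cream and MC2-01 Vehicle will be assigned in a randomized sequence to the test sites", and that each subject will "receive a randomization code, indicating application placement of the study materials". The Day 1 text in Protocol 3.5.1 describes the code in the same terms: "randomization code, indicating application placement of the study products". Protocol 3.4.5.1 adds that "study product placement on the left side will be the same as on the right side", so one binary choice of order settles every product placement.

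SAP Listing 16.1.7 agrees. Its shell has two randomized columns, Site 1 and Site 2, with the key "A = MC2-01 cream; B = MC2-01 vehicle". It has no column for the irradiated set.

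On irradiation, Protocol 3.1 says "One set of patches on the back will be designated for irradiation after approximately 24 hours" and the Induction procedures in Protocol 3.5.1 say "One set of patches will be assigned for irradiation and the other will remain non-irradiated". Neither gives a method.

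SAP 11.8 (Local Tolerability Assessments) plans to compare "each test sample irradiated versus non-irradiated", and SAP 11.7 names the same pairs for the non-parametric fallback. The ANOVA has effects for subject and treatment only. Pairwise tests follow only if the overall test rejects at the 5% level.

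**The concern.** Protocol 3.2 relies on each product having an irradiated and a non-irradiated site as its built-in control. That pair separates a reaction that needs light from one that does not. Randomization balances position for cream against vehicle. Nothing in the documents balances it for irradiated against non-irradiated.

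If staff always irradiate the same set, position and light cannot be told apart within a product. A constant difference between positions, for example in skin sensitivity, tape tension, friction or reading order, would then look like a light effect or mask one. The same difference also enters the diagnosis. Under Protocol 3.5.7.1, when both sites of a product react, the irradiated site must be at least one grade more intense at Rechallenge before photosensitivity is suspected.

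**Working it through.** The plan gives no figure to reproduce. The 50 evaluable subjects are justified by convention (Protocol 4.2, SAP 11.9), with no effect size, SD or power.

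**Step 1: what the code can and cannot balance.**

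| Contrast | Balanced by the A/B order? |
|---|---|
| Cream vs vehicle, same irradiation status | Yes |
| Irradiated vs non-irradiated, same product | No; depends on how the set is chosen, which is not stated |

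The layout does not settle the matter. Protocol 3.1 puts all four Induction sites on one side of the back and the Challenge sites on the other. The left/right rule in Protocol 3.4.5.1 and the reference to irradiated and non-irradiated sides in SAP 11.8 can be read as one side irradiated and the other not. On either reading, the irradiated set occupies a position that the stated code does not randomize.

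**Step 2: bias if the set is fixed.** Let δ be the mean score difference between the two positions and τ the true light effect. The irradiated minus non-irradiated contrast then estimates τ + δ. The subject term removes only what is common to all of a subject's sites, and the treatment term absorbs δ. The bias is therefore δ in full.

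**Step 3: size under assumptions.** Inputs from the documents:
- 50 subjects
- four product sites at Induction
- subject and treatment ANOVA, residual df = 49 × 3 = 147
- 5% F gate before the pairwise tests

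Inputs assumed (not in the documents):
- δ = 0.05 or 0.10 points, the same for both products
- SD of within-subject differences 0.3 or 0.5
- normal scores
- two-sided 5% pairwise tests
- no light effect, τ = 0

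The standard error of the contrast is SD/√50, which is 0.3/7.071 = 0.0424 or 0.5/7.071 = 0.0707. The noncentrality is δ divided by that. The ungated rate comes from the noncentral t with 147 df. The gated rate comes from simulating the ANOVA with the F gate (40,000 runs per row).

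| δ | SD | Noncentrality | LSD test alone | With F gate |
|---|---|---|---|---|
| 0 | any | 0 | 5% | about 2% |
| 0.05 | 0.5 | 0.71 | 11% | about 5% |
| 0.05 | 0.3 | 1.18 | 22% | about 14% |
| 0.10 | 0.5 | 1.41 | 29% | about 21% |
| 0.10 | 0.3 | 2.36 | 65% | about 61% |

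The relevant column is the last, because the SAP plans the gate.

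**Step 4: the same scenarios with the irradiated set randomized 25/25.** The mean bias is about 0. The rejection rate is 1% to 2% with the gate and 4% to 5% without it.

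**The case against.** A reader might infer that the documents show a fixed, non-random irradiated set, and that the contrast therefore is confounded. They do not support that. They are silent on the method, and Listing 16.1.7 is a mock shell: a missing column does not prove a missing procedure. The set may be alternated or randomized in practice.

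A reader might also take the table as the trial's real error rate. It assumes no light effect. Induction uses 2 times the MED, and one MED is by definition the exposure that produces minimal erythema, so some irradiated versus non-irradiated difference is plausible at vehicle sites too, even with readings at 48 or 72 hours. If such an effect exists, rejecting is not an error and the harm is a modestly biased estimate. This stands. It weighs less at Challenge, where the full-spectrum dose is 0.5 times the MED after 6 J/cm² of UVA, but no inferential test is planned there.

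The consequences are also limited:
- Cream versus vehicle on irradiated skin, which separates product from light alone, is planned and protected by the A/B order.
- SAP 11.1 calls the Induction analysis supportive, and Protocol 4.6.2 says photosensitivity is not determined by statistical methods.
- A mean shift of 0.05 to 0.10 is far below the one-grade rule for an individual subject.
- Uniform skin colour, exclusion of damaged skin and baseline site checks reduce position differences.

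All of this stands, and it limits the severity. It does not close the gap. None of these measures balances position, and cream versus vehicle does not replace the within-product contrast. Comparing the irradiated minus non-irradiated difference between cream and vehicle would cancel a position effect common to both, but the SAP does not plan that comparison.

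**Conclusion.** The point holds as a conditional one. The stated code covers product order only, the choice of irradiated set is unspecified, and the planned within-product contrast is therefore not shown to be protected by randomization. If the set is chosen by fixed convention, a position difference enters that contrast one-for-one.

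Under the assumed shifts and SDs and no light effect, the gated false-rejection rate is about 5% to 14% (0.05 points) or about 20% to 60% (0.10 points), against about 2% with no shift. The shift, the SD and the absence of a light effect are all assumptions, so these rates show sensitivity and do not predict the trial's error rate. At Induction the likely harm is bias in a supportive estimate. The effect on the diagnosis is indirect, through the irradiated versus non-irradiated comparison at Rechallenge. The documents do not support a claim that the photosensitization conclusion is invalid. This is an inexpensive design improvement that should be made.

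**What to change.** Extend the code from two to four balanced sequences: product order (AB or BA) by which set is irradiated. Apply it at Induction and Challenge, and carry it to any Rechallenge, where the one-grade rule is used. A separate draw for Challenge is optional. State the method in Protocol 3.4.5.1, align the layout wording in Protocol 3.1 and 3.4.5.1 and SAP 11.8, and add the irradiated set to Listing 16.1.7.

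Sample size, visits, product amounts and UV exposure do not change. The cost is a new randomization list, one listing column, and a check of the irradiated set for each subject before each exposure. That check matters, because a mix-up would irradiate a site meant to serve as the non-irradiated control.

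If conduct is already fixed, report which positions were irradiated for each subject and state the limitation. As the procedures are ordered, the Day 2 reading precedes any product-site irradiation, so comparing the two sets at that reading gives a direct, though limited, look at position.
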